# 1. INTRODUCTION

#### 1.1 **Objectives**

The primary objective of this study is to determine the efficacy of 8 mg/day (4 mg/breast) of BHR-700 gel compared to placebo for reducing breast tissue density in women identified as having dense breast tissue upon analysis of screening mammography using the Food and Drug Administration (FDA) cleared Cumulus 2D software..

#### 1.2 Design

This is a multi-center, randomized, double-blind, placebo-controlled study in women identified as having dense breast tissue upon screening mammography.

Subjects who give informed consent will have screening evaluations, including hormone measures of FSH, Estradiol and Estrone to determine menopausal state. Those subjects meeting entry criteria, will be stratified, based on their hormone levels, into pre/peri and post menopause groups and randomized within those groups 2:1 to receive either 8 mg/day (4 mg/breast) BHR-700 gel or placebo for up to 52 weeks. At the Principal Investigator's (PI) discretion, subjects may be allowed to reduce the dose to 4 mg/day (2 mg/breast) in cases of intolerance.

Subjects will apply the gel to both breasts once per day. The first dose will be applied under the supervision of the PI/designee. Subsequent doses will be self-administered daily by the subject until she has completed 52 weeks of study drug administration. Study drug compliance will be checked at each study visit. Subjects will be asked to capture daily gel administration in a diary and drug canisters will be weighed on release to the subject and on return. The canister weight will be recorded in grams. If the study drug is discontinued or interrupted, the reason(s) will be recorded. During treatment period, subjects will be evaluated at Day 1 and every 13 weeks (±2 weeks) thereafter.

A planned sample size of 330 women, identified as having dense breast tissue upon screening mammography, will be randomized to receive either BHR-700 gel or placebo (at 2:1 ratio). Considering an attrition rate of approximately 15%, it is expected to have 272 evaluable women (4-OHT: 181 & Placebo: 91) who will have both baseline and 52 week measurements of percent mammographic density (MD) of the breast.

Subjects who complete the double-blind phase of the study will be offered entry into an open-label follow-up period for an additional 52 weeks.

# 1.3 Change in Study Conduct

The study was early terminated. Following careful consideration and review of the development program for BHR700 (4-Hydroxytamoxifen Gel, 4-OHT), it was determined that breast density reduction may not be the optimal surrogate marker to support drug development for a target indication of the reduction of the risk of breast cancer.

Planned analyses will be conducted using data available in the clinical database. The sample size of the study may no longer be powered due to the lower number of subjects and shorter duration of treatment for a large proportion of subjects due to the early termination of the study. Therefore, the

interpretation of the analysis results will be cautious. Moreover, the emphasis of the statistical analysis will be on descriptive statistics, rather than hypothesis testing.

# 2. ELABORATION OF STUDY PROTOCOL

#### 2.1 Study Populations

Three analysis populations will be defined and analyzed:

- 1. Intent-to-treat (ITT) population will contain all subjects who are randomized into the study. All efficacy parameters will be analyzed using the ITT population. In the case of a subject who was randomized but did not take the study drug, the analysis will be performed for this subject using the randomized treatment.
- 2. Per-protocol (PP) population will contain all ITT subjects who completed Week 52 assessments and do not have any major protocol deviation. The major protocol deviations will be identified by BH Ireland before the database is locked and unblinded.
- 3. Safety population will contain all subjects who receive at least one dose of study drug. All safety parameters will be analyzed using safety population.

# 2.2 Study Endpoints

#### 2.2.1 Primary Endpoint

Primary endpoint is the percentage reduction of mammographic left breast tissue density on a follow-up mammogram compared to the baseline mammogram after 52 weeks of treatment.

A comparison of percentage reduction in breast density between BHR-700 gel and placebo treatment groups at 52 weeks using the FDA-cleared Cumulus 2d software will be performed.

The primary endpoint will be analyzed for blind treatment phase only.

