1.3 Study Synopsis

Study Title:	A Randomized, Double-Blind, Placebo-Controlled Trial of
~~~~~~	4-Hydroxytamoxifen Gel for Reducing Breast Tissue Density in
	Women with BI-RADS Breast Density Categories C or D
Development Phase:	Phase 3
Investigational Product	BHR-700, 4-Hydroxytamoxifen (afimoxifene) gel
(IP):	
Active Pharmaceutical	4-Hydroxytamoxifen (4-OHT)
Ingredient (API):	
Study Centers:	Multicenter study conducted in approximately 25 centers
Study Duration:	Up to 110 weeks per subject: 2 weeks screening, 52 weeks blinded
	treatment period with an optional 52 weeks open-label extension.
Study Objective	
Primary:	To determine the efficacy of 8 mg/day (4 mg/breast) of BHR-700 gel
	compared to placebo for reducing breast tissue density in women
	identified as having dense breast tissue upon analysis of screening
	mammography using the Food and Drug Administration
	(FDA)-cleared Cumulus 2D software.
Study Endpoints	
Primary:	The percentage reduction of mammographic breast tissue density on
•	a follow-up mammogram compared to the baseline mammogram
	after 52 weeks of treatment.
Secondary:	Incidence and severity of adverse events (AEs) with special attention
J = 1 = 1 = 1	given to uterine abnormalities, cardiovascular events,
	thromboembolic events, and incidence of vasomotor symptoms ("hot
	flush").
	Change in serum concentration of sex hormone binding globulin (SHBG).
	Change in serum concentration of: cholesterol, triglycerides, high-density lipoprotein (HDL), and low-density lipoprotein (LDL).
	Change in serum concentration of Protein C-activity, Protein S- activity, Antithrombin 111 antigen, and Activated Protein C resistance (APCR).
	Change in serum concentration of select bone biomarkers CTx and BSAP.
	Plasma concentrations of the E and Z isomers of 4-OHT.
Study Design	
Methodology:	This is a multi-center, randomized, double-blind, placebo-controlled study in women identified as having dense breast tissue upon screening mammography.
	Subjects who give informed consent will have screening evaluations, including hormone measures of FSH, Estradiol, Estrone and LH to

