	determine menopausal state. Some subjects may require a mammogram to be made at this stage because they do not have a mammogram that fulfills the necessary criteria (format or time period). Those subjects meeting entry criteria, will be stratified, based on their hormone levels, into pre/peri and post menopause groups and randomized within those groups 2:1 to receive either 8 mg/day (4 mg/breast) BHR-700 gel or placebo for up to 52 weeks. At the Principal Investigator's (PI) discretion, subjects may be allowed to reduce the dose to 4 mg/day (2 mg/breast) in cases of intolerance.
	Subjects will apply the gel to both breasts once per day. The first dose will be applied under the supervision of the PI/designee. Subsequent doses will be self-administered daily by the subject until she has completed 52 weeks of study drug administration. A diary will be kept by the subject to monitor compliance, the start and stop dates for the subject's last menstrual cycle and any breakthrough bleeding experienced excluding days of normal menses.
	Subjects who complete the double-blind phase of the study will be offered entry into an open-label follow-up period for an additional 52 weeks.
	While on treatment, subjects will be evaluated at Day 1 and every 13 weeks thereafter.
Number of Subjects:	A planned sample size of 330 women, identified as having dense breast tissue upon mammography, will be randomized to receive either BHR-700 gel or placebo (2:1 distribution). Considering an attrition rate of approximately 15%, the expectation is to have 272 evaluable women (4-OHT: 181 & Placebo: 91) who will have both baseline and 52 week measurements of percent mammographic density (MD) of the breast.
Inclusion Criteria:	
 
Healthy women age 35 – 75 years with either heterogeneously dense (C) or extremely dense (D), breast tissue on 2D mammography, based on American College of Radiology (ACR) Breast Imaging-Reporting and Data System (BI-RADS©) fifth edition classification) in either breast within 3 months prior to randomization. Mammogram with BI-RADS final assessment category 1 or 2 (negative or benign findings).
 
If the woman is of childbearing potential, she must have a documented negative urine pregnancy test at time of screening and randomization and no plans to become pregnant for the duration of study participation.
 
Ability to understand and the willingness to sign a written informed consent document.
 

	1

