# Table 1. ACR BI-RADS[©] Breast Tissue Composition

Approximately 330 subjects will be enrolled at approximately 25 sites located in the U.S. and Europe. Subjects who give informed consent will have screening evaluations, including hormone assessments of FSH, Estradiol, Estrone and LH to determine menopausal state. Those subjects meeting entry criteria, will be stratified, based on their hormone levels into either pre/peri or post-menopausal groups and randomized 2:1 within those groups to receive either 8 mg/day (4 mg/breast) 4-OHT or matching placebo for up to 52 weeks.

Subjects will apply the investigational gel to both breasts once per day. The first dose will be applied under the supervision of the Principal Investigator (PI) or designee. Subsequent doses will be self-administered at approximately the same time daily, after showering, by the subject until she has completed 52 weeks of study drug administration. There will be, in addition, an optional 52 weeks of open-label treatment for those subjects who choose to continue treatment. Subjects will capture daily gel administration in a diary to monitor compliance.

While on treatment, subjects will return to the clinic for study assessments, a review of AEs and to re-supply study gel at 13, 26, 39, weeks and at 52 weeks for those subjects who have agreed to take part in the open-label phase of the study. A schedule of study assessments is shown in Appendix 1.

During the study, in a case of significant changes in bleeding pattern or other signs/symptoms which could be related to endometrial pathology, the Investigator will perform a uterine ultrasound followed by an endometrial biopsy if indicated.

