## 5.0 SUBJECT SELECTION AND WITHDRAWAL

## 5.1 Inclusion Criteria

 Healthy women age 35 – 75 years with either heterogeneously dense (C) or extremely dense (D) dense breast tissue on 2D mammography, based on ACR BI-RADS© fifth edition classification, within 3 months prior to randomization. Mammogram with BI-RADS final assessment category 1 or 2 (negative or benign findings).

- 2. If the woman is of childbearing potential, she must have a documented negative urine pregnancy test at the time of screening and randomization and no plans to become pregnant for the duration of study participation.
- 3. Ability to understand and the willingness to sign a written informed consent document.

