#### 8.8 Mammogram

A bilateral mammogram with both the raw and processed 2D image DICOM files needs to be performed within 3 months prior to randomization. The same (make/model/serial number) mammography machine must be used for the Week 52 and if the subject is participating in the Open-Label phase, the Week 104 mammogram. If the mammogram is older than 3 months but less than 18 months, or it cannot be provided in the format required for the study, the mammogram can be repeated to meet the study entry requirement after informed consent has been obtained. Assuming the original mammogram has been made within 3 months before the date of randomization, the BI-RADS classification of this original mammogram will be used to assess and demonstrate the eligibility of the subject on inclusion criterion 1, a BI-RADS assessment C or D. The repeat mammogram will be used for determining the baseline density measurements, but not for re-assessment and/or confirmation of the BI-RADS criterion.

The mammography report must also be obtained. The breast density classification of C (heterogeneously dense) or D (extremely dense) should be recorded in the subject's study chart.

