# 2.3 Sample Size

Assuming a reduction from baseline in breast density of 6% on active and 2% on placebo, with a common standard deviation of 8%, a sample size of 272 subjects will achieve a power of 90%, using a two sample, two-sided t-test at a significance level of < 0.01. Considering an attrition rate of 15%, 330 subjects are planned for enrollment in this study.

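### The SAP limits the primary density endpoint to the left breast without giving a reason or listing the change, which gives up precision that a two-breast mean would recover in any ad-hoc analysis

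*SAP*

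**What the plan says.** **Endpoint.** SAP 2.2.1 fixes the side: "Primary endpoint is the percentage reduction of mammographic left breast tissue density on a follow-up mammogram compared to the baseline mammogram". The next sentence of that section, on the between-group Cumulus comparison, names no side, and neither do the density items in SAP 2.2.2. In the protocol synopsis (1.3) the primary endpoint begins "The percentage reduction of mammographic breast tissue density on" and continues without a side. The primary objective (protocol 3.0) and the primary outcome measure (protocol 9.1) name none either.

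**Treatment and imaging.** Protocol 4.0: "Subjects will apply the investigational gel to both breasts once per day". Protocol 8.8: "A bilateral mammogram with both the raw and processed 2D image DICOM files needs to be performed within 3 months prior to randomization". The same section requires the same machine at Week 52. The Week 52 visit in 7.3 asks for a mammogram without repeating that it is bilateral.

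**Eligibility.** The synopsis asks for category C or D "in either breast within 3 months prior to randomization". Protocol 5.1 has "fifth edition classification, within 3 months prior to randomization" and does not mention either breast.

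**Sample size.** SAP 2.3: "Assuming a reduction from baseline in breast density of 6% on active and 2% on placebo", "with a common standard deviation of 8" percent. It does not say whether this SD belongs to one breast or to the mean of two.

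**Status.** Protocol 9.1 gives the SAP precedence on analyses. SAP 1.3 reports early termination. SAP 3.3.2 plans no efficacy analysis for the report but allows ad-hoc density analyses after database lock, and SAP 3.8 repeats this. SAP 4.2.3 keeps a breast density listing with no side stated. SAP 3.8, which records changes from the protocol analysis, does not mention the left breast.

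**The concern.** Because the SAP prevails on analyses, the single word naming the left breast becomes the operative primary definition. It narrows an endpoint that the protocol left general, in a trial that treats both breasts and images both at baseline. No reason is given and no rule is stated for right-breast readings. The SAP is also uneven within itself: the primary Cumulus result is left-only, while the secondary Cumulus result has no stated side.

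Two things are at stake. The first is precision: one breast per woman leaves reader and positioning error unaveraged when a second reading may be available from images already taken. The second is pre-specification: if density is analysed ad hoc after lock, an unexplained side in one sentence and no side in the next leaves the choice open when the data can be seen.

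**Working it through.** **Inputs from the documents.** Difference 6 − 2 = 4, SD 8, two-sided t-test at 0.01, 181 and 91 evaluable women (SAP 1.2 and 2.3).

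**Input not in the documents.** The left-right correlation of change, ρ. It is an assumption, shown from 0.9 to 0.5. The calculation also assumes the same SD and the same treatment difference on each side.

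**Step 1: reproduce the plan.** Standard error = 8 × √(1/181 + 1/91) = 8 × 0.1285 = 1.028. Noncentrality = 4 / 1.028 = 3.89 on 270 degrees of freedom. Noncentral-t power is 90.2%. The normal approximation needs 270 women and the exact t-test at 2:1 needs 273, against the stated 272. The plan's figure reproduces, and it does not depend on which breast is measured.

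**Step 2: variance of a two-breast mean.** SD of mean = SD of one breast × √((1 + ρ)/2). The gain in information over one breast is 2/(1 + ρ) − 1.

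**Step 3: two readings of SD 8,** both at 181/91.

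| ρ (assumed) | Information gain | SD 8 is one breast: SD of mean | Power of two-breast mean | SD 8 is two-breast mean: SD of left only | Power of left only |
|---|---|---|---|---|---|
| 0.9 | 5% | 7.80 | 91.8% | 8.21 | 88.4% |
| 0.8 | 11% | 7.59 | 93.3% | 8.43 | 86.3% |
| 0.7 | 18% | 7.38 | 94.7% | 8.68 | 83.9% |
| 0.5 | 33% | 6.93 | 97.1% | 9.24 | 78.0% |

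Under the first reading, left-only already has the planned 90.2%, and averaging adds 1.6 to 6.9 percentage points. Under the second, left-only falls 1.8 to 12.2 points below 90.2%. The documents do not say which reading applies.

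**Step 4: what these figures describe.** They use the planned 272 evaluable women. SAP 1.3 says the actual number is lower and many women were treated for less time, so the table shows the relative cost of using one side. It does not give the power of the trial as it ended.

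**The case against.** The strongest reply is early termination. With no efficacy analysis in the report and an emphasis on description, the choice of side changes no planned result. That stands, and it confines the point to ad-hoc analyses and the density listing.

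A second reply is that naming a side is legitimate detail: it sits in the SAP section that elaborates the protocol, the SAP has precedence, and SAP 3.8 deals only with consequences of termination. This stands in part. A single breast is an acceptable choice if it is justified and disclosed, and here it is neither.

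A third reply is that redefining the variable now is itself a late change. That is fair. It is why the definition must be fixed before any density analysis and left-only retained beside it.

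A reader might also infer more than the documents support:

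- *Half the data are discarded.* This is true at most of the count of breast measurements in the primary variable. The information forgone is about 5% to 33% over the assumed range; a 100% gain would need ρ = 0. Nor do the documents say that right-breast readings are dropped, since the secondary endpoints and the listing name no side.
- *Women are scored on a breast that did not qualify.* This rests on the synopsis wording alone. Protocol 5.1 does not repeat it, Table 1 grades the breasts together, and 8.8 speaks of one density classification per woman. No count of discordant women is given. Averaging would not cure it either, because the mean still includes any non-qualifying breast.

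**Conclusion.** The point holds as one of definition and precision. SAP 2.2.1 narrows the primary endpoint to the left breast, unexplained and unlisted, although both breasts are treated and the baseline images cover both.

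A reader might go on to infer a biased comparison or an underpowered design, and neither is supported. The same side is used in both randomised arms, and 272 reproduces at 90.2% if SD 8 is a one-breast figure. Left-only falls below plan only if SD 8 describes a two-breast mean.

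The size is modest: power of 91.8% to 97.1% instead of 90.2% on one reading of SD 8, or 88.4% to 78.0% for left-only on the other. All of these rest on an assumed ρ of 0.9 to 0.5, equal SDs and effects on the two sides, and the planned numbers. After early termination the practical reach is limited to ad-hoc density analyses.

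**What to change.** Before any ad-hoc density analysis:

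1. Define the density variable in SAP 2.2.1 as the per-woman mean of left and right percent density, wherever bilateral images exist at both time points. State the rule for women with only one side available.
2. Keep left-only as a sensitivity analysis. If the left breast is retained as the main variable instead, give the reason.
3. State in SAP 2.3 whether SD 8 refers to one breast or to the mean of two.
4. Record the departure from the protocol endpoint in SAP 3.8, and name the side in SAP 2.2.2 and in the density listing.
5. Separately, reconcile the synopsis with protocol 5.1 on whether category C or D in either breast is enough. Averaging does not settle this.

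The cost is SAP text plus Cumulus reads of the second side by the same blinded central reader, where these do not already exist. It must first be confirmed that the Week 52 images are bilateral and that the reader is still available, since the documents state neither. No new mammogram or participant is needed.

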#### 2.2.2 Secondary Endpoints

- 1 The percentage reduction in breast density at Week 52 using two breast density measurement methods (Cumulus versus Volpara).
- 2 The percentage of women who underwent a change in BI-RADS category when comparing pre-and post-treatment measurements.
- 3 The percentage of women with a ± 10% absolute decrease in quantitative mammographic density (Cumulus) between baseline and 52 weeks,
- 4 Change in serum concentration of: cholesterol, triglycerides, high-density lipoprotein (HDL), and low-density lipoprotein (LDL).
- 5 Change in serum concentration of sex hormone binding globulin (SHBG).
- 6 Change in serum concentration of Protein C-activity, Protein S-activity, Antithrombin 111 antigen, and Activated Protein C resistance (APCR).
- 7 Change in serum concentration of select bone biomarkers CTx and BSAP.
- 8 Incidence and severity of AEs and laboratory values.
- 9 The menstrual cycle of premenopausal women.
- 10 Pharmacokinetic (PK) plasma concentration of the E and Z isomers of 4-OHT after 13, 26, 52, 78, and 104 weeks of application of 4 mL BHR-700 gel to the breasts.

The secondary endpoints are for both blind and open-label treatment phases.

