#### 3.0 STUDY OBJECTIVES & PURPOSE

The overall purpose of this study is to evaluate whether daily application of 8 mg (4 mg/breast) of 4-OHT lowers breast density in women with mammographically dense breast tissue.

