## Secondary Objectives:

- 1. To compare the change in percent mammographic density from Baseline to the Week 52 mammogram in women applying 8 mg 4-OHT vs. placebo, using two breast density measurement methods (Cumulus versus Volpara).
- 2. To compare the percentage of women who underwent a change in BI-RADS category when comparing pre-and post-treatment measurements for recipients of 4-OHT and placebo.
- 3. To compare the percentage of women with a  $\pm$  10% absolute decrease in quantitative mammographic density (Cumulus) between baseline and 52 weeks, when comparing between the recipients of 4-OHT and placebo.
- 4. To describe the symptoms assessed by laboratory toxicity assessments complete blood count (CBC) w/diff, blood chemistry, coagulation factors, lipid panel, liver function tests, sex hormone binding globulin (SHBG), and bone biomarkers.
- 5. To determine the safety and tolerability of 8 mg/day of 4-OHT after 52 weeks of administration to the breasts such as AE collection, effects on menstrual cycle, and laboratory values.
- 6. To determine whether 8 mg/day of 4-OHT will disrupt the menstrual cycle of premenopausal women.
- To determine the plasma concentration of the E and Z isomers of 4-OHT after 13, 26, 52, 78, and 104 weeks of application of 4 mL BHR-700 gel to the breasts.

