#### 3.3.2 *Efficacy Analysis*

Since the study was terminated early, no efficacy analysis planned for the study report, while safety data will be summarized and reported in the study report.

However, with careful review of the mammographic data after database lock, mammographic efficacy data may be analyzed as ad-hoc analyses as necessary.

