# 4.2.3 Listings of efficacy and PK/PD data

- 21. Listing [LEF01a] Breast Density (Blinded Phase) ITT Population
- 22. Listing [LBR01a] Breast Tissue Composition BI-RADS Grade (Blinded Phase) ITT Population
- 23. Listing [LHR01a] Hormones Results (Blinded Phase) ITT Population
- 24. Listing [LBB01a] Bone Biomarkers (Blinded Phase) ITT Population
- 25. Listing [LCR01a] Coagulation Parameters (Blinded Phase) ITT Population
- 26. Listing [LPK01a] Plasma PK Concentrations (Blinded Phase) ITT Population
- 27. Listing [LEM01a] Endometrial Results (Blinded Phase) ITT Population (only if data available)

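### The BI-RADS secondary endpoint names no direction, so a move from C to D counts the same as a move from D to C or C to B

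*SAP*

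**What the plan says.** Secondary objective 2 in Protocol 3.0 reads "To compare the percentage of women who underwent a change in BI-RADS category when comparing pre-and post-treatment measurements for recipients of 4-OHT and placebo". SAP 2.2.2 item 2 carries it over as "The percentage of women who underwent a change in BI-RADS category when comparing pre-and post-treatment measurements". No other section of either document adds a direction, a minimum number of categories, a responder rule or a shift table.

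The surrounding text does have a direction. Protocol 3.0 gives the purpose as finding out whether daily 4-OHT "lowers breast density in women with mammographically dense breast tissue". In SAP 2.2.2, item 1 is a percentage reduction, and item 3 is an "absolute decrease in quantitative mammographic density (Cumulus) between baseline and 52 weeks", although a stray ± sign precedes its threshold. Eligibility under Protocol 5.1 requires "either heterogeneously dense (C) or extremely dense (D) dense breast tissue on 2D mammography".

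On what will be produced, SAP 3.3.2 states that there is "no efficacy analysis planned for the study report" because the study stopped early. Mammographic data may be analysed ad hoc after database lock and, under SAP 3.8, reported separately. The only planned output on this endpoint is listing LBR01a in SAP 4.2.3, "Breast Tissue Composition BI-RADS Grade (Blinded Phase) ITT Population".

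**The concern.** The scale has four ordered grades, and the trial wants women to move down it. A woman who starts at C can move either way, while a woman who starts at D can only stay or move down. The endpoint as worded adds the two directions together. A treatment that lowers density should produce more downward moves and, if anything, fewer upward ones. In a count of all moves, the second effect is subtracted from the first.

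What is at stake is how a BI-RADS comparison would read. If the ad hoc analysis applies the written definition, its percentage includes women who got worse. If the analyst restricts it to decreases, that choice is made after lock, with the data available and no written rule behind it. The problem does not depend on a hypothesis test, because an undirected percentage is hard to interpret as a descriptive figure too.

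**Working it through.** **The plan's own figure.** The documents size the trial for the primary Cumulus endpoint only: reductions of 6% v 2%, SD 8%, two-sided alpha 0.01, power 90%, allocation 2:1 (SAP 2.3 and 1.2). The normal approximation gives a placebo arm of (2.576 + 1.282)² × 8² × (1 + 1/2) / 4² = 89.3, so 90, and a total of 270. The noncentral t gives 90.2% power at 181 and 91. The stated 272 is reproduced, but it says nothing about BI-RADS grades. No rate, effect or power is given for that endpoint.

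**Algebra.** Let d1, d0 be the proportions moving down and u1, u0 the proportions moving up, on active and placebo. The endpoint as worded compares d1 + u1 with d0 + u0, so its difference is

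(d1 − d0) − (u0 − u1).

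Three results follow:
- With no upward moves, the two definitions agree.
- With equal upward moves in both arms, the difference is unchanged, but both proportions lie closer to one half, so the variance is larger and power is lost.
- With more upward moves on placebo, the difference itself shrinks by u0 − u1.

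**Illustration.** The rates are assumed. The numbers per arm are the original evaluable target of 181 and 91 (SAP 1.2), and the level is two-sided 5% (SAP 3.1). Power = Φ[(p1 − p0 − 1.96 × SE0) / SE1], where SE0 = √[p(1 − p)(1/181 + 1/91)], p is the pooled proportion, and SE1 = √[p1(1 − p1)/181 + p0(1 − p0)/91]. Decreases are 25% v 10% throughout.

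| Increases, active v placebo | Any change | Difference | SE0 | SE1 | Power |
|---|---|---|---|---|---|
| none | 25% v 10% | 15 points | 0.0514 | 0.0450 | 86% |
| 5% v 5% | 30% v 15% | 15 points | 0.0556 | 0.0506 | 79% |
| 10% v 10% | 35% v 20% | 15 points | 0.0589 | 0.0549 | 74% |
| 5% v 10% | 30% v 20% | 10 points | 0.0568 | 0.0540 | 42% |
| 5% v 15% | 30% v 25% | 5 points | 0.0579 | 0.0568 | 13% |

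The first row is also the power of a decrease-only definition in every scenario, because that definition ignores the upward moves. For the fourth row: (0.10 − 1.96 × 0.0568) / 0.0540 = −0.21, and Φ(−0.21) = 0.42.

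**The case against.** The strongest reply is that nothing planned depends on this wording. The SAP was written for a study that had already stopped. It drops efficacy analysis from the report, puts the emphasis on descriptive statistics (SAP 1.3), and keeps BI-RADS only as a listing of grades, from which the direction of each woman's change can be read. That stands, and it confines the consequence to an ad hoc analysis.

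The power figures are also open to challenge. SAP 1.3 says that the sample may no longer be powered, because there are fewer subjects and many had shorter treatment, so 181 and 91 do not describe the women actually available. The rates are assumed, and the steeper losses need placebo women to worsen noticeably more often than treated women. The sizing assumption that placebo density falls by 2%, and the statement in Protocol 2.1 that density declines with age, both point away from frequent upward moves. Only women at baseline C can move up at all. This also stands. The table shows a mechanism and a range, not an expected loss.

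A reader might go further and infer that the endpoint could favour placebo when the gel works, or that it leaves the density objective unsupported. The documents do not bear out either inference. A reversal needs u0 − u1 to exceed d1 − d0, which in the illustration means a placebo excess of upward moves above 15 points; in every row of the table active still leads. The density objective rests on the Cumulus primary endpoint, and BI-RADS change is one supportive item among ten.

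It may also be said that a reduction was obviously intended. That is likely, but neither document says so, and the neighbouring items show that direction was written in where it was thought of.

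**Conclusion.** The point holds as a defect of definition. Both documents count any change of category, which sets the endpoint partly against the trial's stated purpose. This conclusion rests on the wording alone and needs no assumed rates.

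The size cannot be fixed from the documents. Under the assumed decreases of 25% v 10% at the original target, the loss runs from nothing (no upward moves), through 86% to 79% (5% upward in both arms), to 86% to 42% (5% v 10% upward). The difference between arms is diluted only where upward moves are more frequent on placebo.

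The practical reach is limited to the comparison named in the protocol objective and to any ad hoc mammographic analysis. The planned study report is not affected. The definition should be corrected before any such analysis is run, but it does not undermine the trial's main efficacy question.

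**What to change.** Define the event as a decrease of at least one BI-RADS density category (A to D) from the baseline grade. Report the percentage with an increase separately, and show a shift table of baseline by post-treatment grade for each arm.

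Three details belong in the same text:
- Say that the density category is meant, because Protocol 5.1 also uses BI-RADS for the final assessment category.
- State which mammogram supplies the baseline grade. Protocol 8.8 uses a repeat mammogram for baseline density but not for re-assessing the BI-RADS criterion.
- Keep true Week 52 readings apart from early End of Study readings. SAP 3.8 pools them under the nominal Week 52 visit, and women who stopped early had less time to change category.

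Write the definition into the SAP or the ad hoc analysis plan before grades are viewed by arm. If that point has passed, label the directed analysis as post hoc. The cost is one line of text for the event definition, these clarifications, and one table built from the grades already in LBR01a. No new data are needed.
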